# **STUDY SUMMARY**

STUDY TITLE	Adipocytokines and their relationship with		
	obesity and endometrial cancer		
SHORT TITLE	Adipocytokines in endometrial cancer		
STUDY DESIGN	exploratory biomarker study		
STUDY PARTICIPANTS	Study population - patients presenting to		
	Royal Surrey NHS Foundation Trust with		
	endometrial cancer, identified at the MDT		
	Control population - female patients		
	without endometrial cancer, referred for		
	benign condition.		
PLANNED SIZE OF SAMPLE	100-120		
FOLLOW UP DURATION	N/A		
PLANNED STUDY PERIOD	36-48 months		
RESEARCH QUESTION /AIM(S)	To investigate the relationship between		
	adipocytokine level in blood and tissue		
	(endometrial cancer tissue, adipose tissue		
	and lymph node) in patients with		
	endometrial cancer and co-relate with BMI		
	to identify peripheral biomarkers that can		
	be used as prognostic or diagnostic tools		

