Also, in an inflammatory environment, macrophages secrete potent proinflammatory cytokines such as TNF- $\alpha$  and IL-6, which are known to activate numerous transcription factors that regulate the expression of genes involved in immune responses, anti-apoptosis,

angiogenesis, and metastasis. The mechanisms of tumorigenesis are thought to be involved are free-radical production that cause DNA damage and impaired DNA repair.

Research have further suggested that systemic levels of insulin-like growth factor (IGF) is dysregulated in obesity either due to increased IGF production or by down-regulation of IGF binding protein (IGFBP) prodution. IGF 1 is a growth and proliferation promotor and has inhibitory effects on cell death and is a major contributor in many neoplastic transformation.

The above biomarkers are physiologically interrelated and are likely to reflect a more restricted number of underlying biological pathways. Possibly, they work in a synergistic capacity to modulate the risk of developing endometrial cancer. If specific patterns of cytokine expression were found to be predictive of adverse outcome, then the specific receptors may be targeted as a therapeutic option for endometrial cancer. No study so far has looked at all these markers together in the serum and tissue samples of the same endometrial cancer patients to give a more wholesome idea about their effect on tumour genesis, progression and outcome. Therefore, this study is designed to assess the prognostic significance of these six biomarkers in the blood and tissue of endometrial cancer patients and co-relating the levels with their BMI and tumour type, after adjusting for age, parity, smoking status, menopausal status, use of Hormone Replacement Therapy (HRT)/ hormonal contraception, and prevalence of diabetes and hypertension.

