# 4.3. Secondary Outcomes

- 1. To determine if the markers have any prognostic significance by the expression profile with tumour grade, stage and histology.
- 2. To determine if the markers could be used as tools to assess effects of treatment.

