### 5.4. Sample analysis

ELISA will be used to assay bio-marker levels in blood samples.

For tissue analysis we will set up a tissue microarray (TMA). This will allow more uniform staining of the sample for immunohistochemistry with no inter-specimen variation of the staining method. Each case will be reviewed, and the area of interest (tumour) marked on the slide. Cores from the areas of interest will be used to create the microarray block. Sections can then be cut from the microarray block and slides prepared for immunestaining. The advantage of using this method is that the samples are subjected to the same conditions while being stained and the same part of a tumour can be reliably stained for several markers. Tissue sections from the TMA will be used for immune-staining and the expression of the markers of interest will be scored.

Some tests have become available at the University of Surrey laboratory that can be done from the samples that are already being collected to maximise our information on endometrial cancer from the samples already available. These tests will be carried out at the University of Surrey laboratory and will not involve any resource implication on Royal Surrey NHS Foundation Trust.

The additional tests may include - looking at the cancer tissue microenvironment for infiltrating inflammatory cells and / or their secretions or any other adipocytokines. We may also look at the tumour microbiome to look for any commensal bacteria or micro-organism that may have a role in cancer onset, progression and drug response by secretion of small molecules and metabolites. Clinical data which is available on the cases will then be correlated with the histological and immunohistochemical results and statistical analysis will be carried out.

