### 5.5. Data analysis

Standard statistical analytical tools will be used to analyse the data. Relation between different variables will be sought with odds ratio, confidence interval and significance with P value (<0.05 significant). The Mann–Whitney U test will be used to assess differential expression of immune markers between tissue types –blood and tumour tissue. Correlation with clinical characteristics will be determined using univariate log-rank and multivariable Cox proportional hazards adjusting for age, stage, grade and histology. Results will be compared between the study and the control populations.

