# 7.3. Sample size

We will aim to recruit 30-60 patients with diagnosed endometrial cancer in the study. This sample size will also include archived tissue sample (formerly consented and stored in Leggett building for use in future ethical research). We will aim to recruit as many patients in the control population as in the study population, aiming for a total (study + control population) of 100-120 patients.

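### The univariate log-rank test in section 5.5 forces continuous blood markers into groups that the plan does not define, which costs power; univariable Cox regression on the continuous level would avoid it

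*Combined protocol and SAP*

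**What the plan says.** Section 5.5 (Data analysis) gives the time-to-event methods in one sentence: "Correlation with clinical characteristics will be determined using univariate log-rank and multivariable Cox proportional hazards adjusting for age, stage, grade and histology". It sets the threshold as "significance with P value (<0.05 significant", without stating sidedness.

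Section 5.4 (Sample analysis) describes the measurements. For blood, "ELISA will be used to assay bio-marker levels in blood samples". For tissue, after immunostaining of the microarray sections, "the expression of the markers of interest will be scored"; neither the scoring system nor its number of levels is given.

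Section 1 (Background) gives the purpose: "this study is designed to assess the prognostic significance of these six biomarkers in the blood and tissue of endometrial cancer patients". Section 7.3 sets the number of cases: "We will aim to recruit 30-60 patients with diagnosed endometrial cancer in the study", archived samples included. It gives no power, effect size or event count.

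Nowhere do the documents state a cut-point, a rule for forming marker groups, or that markers stay continuous.

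**The concern.** A log-rank test needs groups. An ELISA concentration has none until someone divides it, so the named test cannot be run on any of the six blood markers without a decision that the plan leaves open.

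That matters in three ways:

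- **Power.** Any split into high and low treats all women on one side of the cut as alike. With 30 to 60 cases there is little information to spare.
- **False positives.** A cut settled after looking at the survival curves invalidates the log-rank P value. The plan contains nothing to prevent this.
- **Comparability.** The multivariable Cox model can take the marker as continuous. If it does, the crude and adjusted results for the same marker rest on different codings, and the effect of adjustment cannot be read from comparing them.

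The Study summary aims at markers usable as prognostic or diagnostic tools, so both a missed marker and a spurious one would count.

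**Working it through.** **Inputs from the documents.** 30 to 60 cases (section 7.3); six markers (section 1); 0.05 per test (section 5.5), taken as two-sided. There is no stated power or event count to reproduce.

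**Assumptions.** 20% to 35% of cases have an event. Expected events are therefore 30 × 0.20 = 6 to 30 × 0.35 = 10.5 with 30 cases, and 60 × 0.20 = 12 to 60 × 0.35 = 21 with 60 cases. The log marker is normal, with a true hazard ratio (HR) of 1.5 or 2.0 per SD.

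**1. Information kept by a median split.** For a normal marker, the asymptotic efficiency of a median split relative to the continuous value is 2/π = 0.637. About 36% of the information is lost, and the same power needs π/2 = 1.57 times the events, or about 57% more.

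**2. Events needed for 80% power.** Continuous marker: D = (1.96 + 0.842)² / (ln HR)². Median split: D × π/2.

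- HR 2.0: 7.85 / 0.480 = 16.3, so 17 events; split 16.3 × 1.571 = 25.7, so 26.
- HR 1.5: 7.85 / 0.1644 = 47.7, so 48 events; split 47.7 × 1.571 = 75.0, so 75.

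**3. Power at the planned size.** The formula Φ(√D × ln HR − 1.96) is optimistic with so few events, so power was simulated: exponential event times, Cox score test on the continuous marker against the log-rank test at the median. Ranges run from 20% to 35% with an event.

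| Cases | HR per SD | Continuous | Median split | Loss (points) |
|---|---|---|---|---|
| 60 | 2.0 | 63% to 85% | 41% to 63% | 22 |
| 30 | 2.0 | 34% to 53% | 21% to 35% | 13 to 18 |
| 60 | 1.5 | 29% to 43% | 19% to 30% | 10 to 13 |
| 30 | 1.5 | 16% to 24% | 11% to 17% | 5 to 7 |

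The 30-case, 20% figures are the least stable. If the event count is fixed at exactly six rather than left to vary, the split has only 12% power at HR 2.0 and 5% at HR 1.5.

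**4. False positives if the cut were chosen from the data.** With no true association, taking the cut with the largest log-rank statistic and testing it at a nominal 5% gave:

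- about 23% to 26% significant when the search covered the central 50% of marker values;
- about 34% to 41% when it covered the central 80%;
- about 5% for the continuous test (4.6% to 5.7%).

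**The case against.** **The marker reading is inferred.** Section 5.5 names neither an outcome nor the markers as the log-rank factor. If the factors were stage, grade or histology, they would already be categories. This stands as a caveat. But the preceding sentence concerns immune markers, the Cox model already adjusts for stage, grade and histology, and section 1 gives a prognostic purpose. The marker is the reading that fits.

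**No time-to-event endpoint exists.** The Study summary enters not applicable against "FOLLOW UP DURATION", and section 4.3 frames prognosis differently: "To determine if the markers have any prognostic significance by the expression profile with tumour grade, stage and histology". This stands, and it is the more basic gap. Neither the log-rank test nor Cox regression can be run until an event and time origin are defined. If the plan were instead repaired by relating markers only to grade, stage and histology, the log-rank test would go and this point with it.

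**Staining scores may already form groups.** Accepted. A reader might infer that every marker must be cut. Section 5.4 supports that only for ELISA levels, since a tissue score with few levels could be used as it is or in a trend version of the test.

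**The plan proposes neither a median split nor a search for the best cut.** Correct. Tertiles or a cut fixed in advance are also possible. Leaving the choice open does not, however, remove the need to group.

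**Too few events is the larger limitation.** Largely true: at HR 1.5 the continuous analysis stays below 50% power throughout. That is a reason not to discard further information.

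**Conclusion.** The point holds for the blood markers. The named univariate test requires a grouping that the plan does not define, and even a neutral median split gives up about 36% of the information. Under the assumed event rates this costs about 5 to 22 percentage points of power, most where the study has most chance of finding something (60 cases, HR 2 per SD).

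A reader might infer that the study will report chance findings at a rate of 23% to 41% per marker. The documents do not support that: those figures apply only if a cut is selected from the study data, which the plan does not propose. They show the size of a risk left open, not the error rate of the planned analysis.

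All power figures rest on assumed event rates and hazard ratios and on a normal log marker. The conclusion also depends on reading the marker as the log-rank factor and on the study keeping a time-to-event analysis. Subject to that, a better method is available at almost no cost, and the change should be made even in an exploratory study.

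**What to change.** First define the event and the time origin. Then, in section 5.5, replace the univariate log-rank test with text to this effect:

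> Each blood marker will be analysed by univariable Cox regression with the log2 ELISA level as a continuous term, coded identically in the multivariable Cox model. Results will be given as the hazard ratio per doubling with its 95% confidence interval. Tissue staining scores will enter as an ordered (trend) term. Any Kaplan-Meier curves by marker group are for display only, and no cut-point will be chosen from the study data.

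The staining scale should be named in section 5.4, so that the trend term has a defined meaning.

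**Cost.** A few lines of text and no new samples or data. The continuous term assumes a roughly log-linear effect, and the trend term assumes that steps on the score are comparable. With about 6 to 21 events these assumptions can be checked only weakly, and the report should say so.

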#### 6. STUDY SETTING

Study patients will be recruited when attending a clinic in the department of Gynaecological Oncology at Royal Surrey NHS Foundation Trust. Private consultation rooms are available here for discussing the study, history taking and consenting.

Blood sample will be collected on the day of the surgery when they are in the theatres and then repeated on day 1 post-operative in gynaecology ward and at 3 or 6 months post-surgery follow-up in clinic.

Tissue samples will be obtained from the following areas:

- 1. Adipose tissue from the main theatres at Royal Surrey NHS Foundation Trust
- 2. Uterine cancer tissue and lymph node from the histopathology department after they have finished analysis.

For those women recruited undergoing chemotherapy, blood sample will be procured at initial consultation and after 3rd (with the blood test before the fourth cycle of chemotherapy) and 6th cycles of chemotherapy. This can be performed in the Department of Gynaecological Oncology at Royal Surrey NHS Foundation Trust.

All samples (blood and tissue) will then be transferred to the Leggett Building at University of Surrey for processing and storage following HTA regulations. The samples will be double boxed for transfer. The outside box will be an icebox. The PI will personally transport the tissues by foot from the hospital to the Leggett building as they are very near geographically and it is a short 4 minutes' walk.

Control patients will be recruited when they attend a clinic appointment at Royal Surrey NHS Foundation Trust for any benign condition. Blood sample will be collected during their clinic appointment after written consent. If they are having any uterine surgery, endometrial tissue will be collected after histopathological diagnosis from the histo-pathology department.

Samples will also be stored anonymised (in case of patients who give consent) in Leggett building, University of Surrey following all regulations by HTA) for use in ethics approved future research project.

Historical samples / tissue blocks stored in the oncology department in the Leggett building, University of Surrey, from a previous study will also be used if appropriate consent is in place.

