Tissue samples from patients undergoing surgery will be collected as follows: For the study population, the PI will collect any fresh tissue (adipose tissue) directly from theatre before fixing as it is not needed for establishing diagnosis and the uterine cancer tissue and lymph node will be collected by the PI after histo-pathological examination from the histo-pathology department after the diagnosis is established. For the control population, if they are having uterine surgery, then the PI will collect some endometrial tissue after histo-pathological examination from the histo-pathology department after the diagnosis is established. All tissue processing will adhere to Human Tissue Authority (HTA) guidelines and will be performed at the Oncology laboratory at Leggett building at University of Surrey.

For study population only - the patients will have repeat blood tests (30mls of venous blood taken each time) on day 1 post-surgery and at their 3 or 6 months routine post-surgery follow up appointment. Control population will not have any repeat blood tests.

For the study population, women who are recommended chemotherapy, we will also ask consent to collect demographic data and baseline blood sample (30mls venous blood) at the time of consultation and after 3rd and 6th chemotherapy cycles to assess any changes in the markers that may correlate with progression or regression of disease.

We will also obtain archival serum samples and tissue blocks (of uterine cancer patients consented from a previous study for use during an appropriate ethics committee approved research) to help increase the number of recruitments for this study. Their demographic data with identification log will be made available to the PI only to assess for correlation between their data and the tissue diagnosis during analysis.

Timing of events including telephone contact events:

- 1. Send study Invitation Letter with Appointment Letter.
- 2. Clinic visit where patient is recruited/ phone call follow-up after clinic visit if the PI is not able to attend the clinic.
- 3. Enrolment of participant in study after consent.
- 4. Collection of blood and tissue sample as described above.

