# 5.3. Study flow-chart for patients undergoing chemotherapy (CT)

Procedures	Pre-study	Treatment period		iod
	Screening	Before	After 3rd	After 4th
		starting CT	CT cycle	CT cycle
Visit Number	1	2	3	4
Written informed consent	Х			
Demographic data	Х			
Medical history	Х			
Assessment of inclusion/ exclusion	Х			
criteria				
Protocol restriction and continued	Х	X	Х	Х
eligibility check				
Concomitant medication	Х	Х	Х	X
Taking blood sample		Х	Х	Х
Recording AEs			Continuous	

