#### 7.4.3 Withdrawal of consent

Participants are free to withdraw at any time and without giving a reason. A decision to withdraw or not take part will not affect the standard of care they will receive. Anonymised data or tissue already collected with consent would be retained and used in the study. Anonymised data or tissue already collected with consent would be retained and used in the study. This is because once anonymised, samples and data cannot be linked back to a participant and therefore we are unable to withdraw a participant's anonymised data or samples. No further data or tissue would be collected, or any other research procedures carried out on or in relation to the participant if they withdraw their participation.

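### No blood is specified when chemotherapy ends early, so the final marker change may be observed mainly in women who complete the course

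*Combined protocol and SAP*

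**What the plan says.** Sections 5.1 and 6 describe the same three chemotherapy bloods: one at the initial consultation, then "after 3rd (with the blood test before the fourth cycle of chemotherapy) and 6th cycles of chemotherapy". Section 5.1 gives their purpose: "to assess any changes in the markers that may correlate with progression or regression of disease". They also serve secondary outcome 2 in section 4.3: "To determine if the markers could be used as tools to assess effects of treatment".

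The flow-chart table in 5.3 places the third blood after the 4th cycle, not the 6th.

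The only rule that ends data collection for a participant is in 7.4.3: "No further data or tissue would be collected". It concerns women who withdraw from the study, not women whose chemotherapy stops. Sections 5.1, 5.3 and 6 do not mention a blood at early stopping, at progression or at the end of treatment.

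On analysis, section 5.5 states: "Correlation with clinical characteristics will be determined using univariate log-rank and multivariable Cox proportional hazards adjusting for age, stage, grade and histology". It describes no analysis of within-patient change and no rule for missing samples.

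**The concern.** The last blood depends on the woman reaching a set cycle. Anyone who stops before it, for progression, toxicity or another reason, or whose planned course is shorter, has no scheduled end-of-treatment sample. If progression is among the reasons for stopping, whether the last sample exists depends on the outcome it is meant to track. The final marker change could then describe mostly women who did well enough to finish, with few progressors for comparison. Later analysis cannot recover a blood that was not drawn.

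**Working it through.** The plan states no figure on this point, so there is none to reproduce. The check has two parts.

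**Reading the sections together**

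- A woman who reaches the last scheduled cycle has baseline, post-cycle-3 and final bloods.
- A woman who stops after the post-cycle-3 blood but before the last one has baseline and post-cycle-3. She contributes one on-treatment change but no final change.
- A woman who stops before the post-cycle-3 blood has a baseline only.
- Section 6 links the post-cycle-3 blood to the test done before cycle 4. A woman who stops straight after cycle 3 may have no such test, so she may lose the middle sample too.

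**Illustration of size**

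Section 7.3 plans 30-60 cancer patients including archived samples, with no chemotherapy subgroup size. Every other input below is an assumption.

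1. Stopping unrelated to progression. With per-cycle stopping rate h, the share reaching the blood after cycle k is (1 − h)^k.

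| h | post-cycle 3 | post-cycle 4 | post-cycle 6 | cycle-3 blood but no cycle-6 blood | baseline only |
|---|---|---|---|---|---|
| 2% | 94% | 92% | 89% | 6% | 6% |
| 5% | 86% | 81% | 74% | 12% | 14% |
| 10% | 73% | 66% | 53% | 20% | 27% |

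2. Stopping related to progression. Take 20 women, 25% progressors (5 against 15), with per-cycle stopping of 20% in progressors and 3% in others. Progressors remaining are a = 5 × 0.80^k and others b = 15 × 0.97^k. Power for a 1-SD difference in marker change, two-sided 0.05, normal approximation, is Φ(1/√(1/a + 1/b) − 1.96); the other tail is negligible.

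| Point | Progressors | Others | Progressor share | Power |
|---|---|---|---|---|
| Start | 5.0 | 15.0 | 25% | 0.49 |
| Post-cycle 3 | 2.6 | 13.7 | 16% | 0.31 |
| Post-cycle 4 | 2.0 | 13.3 | 13% | 0.27 |
| Post-cycle 6 | 1.3 | 12.5 | 9.5% | 0.19 |

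With progressor stopping of 10% or 30% per cycle instead, the number with a post-cycle-6 blood is 2.7 or 0.6 of 5.

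3. A cruder range: progressors with a final blood = N × P(progress) × (1 − P(stop before it)). The low end is 10 × 0.2 × 0.1 = 0.2 and the high end is 20 × 0.3 × 0.5 = 3. This counts final samples only and leaves out progressors who have a usable post-cycle-3 blood.

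The choice between the 4th and 6th cycle changes the size of the loss (0.80^4 = 41% of progressors against 0.80^6 = 26%), but not its direction.

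**The case against.** The strongest reply is that sampling at a fixed cycle keeps treatment exposure comparable between women, which is a reasonable choice in an exploratory biomarker study. A last sample taken whenever treatment ends would come early in progressors and late in responders, so its timing would be tied to outcome. Recording the cycle number describes that link but does not remove it, because the cycle number is itself a consequence of progression. This objection stands, and it is why the fix keeps the scheduled bloods and the post-cycle-3 comparison.

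The documents do not support three stronger readings that a reader might infer:

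- That early stoppers leave the progression-or-regression question altogether. Those with a post-cycle-3 blood still supply an on-treatment change.
- That secondary outcome 2 would be answered in completers only. Its wording covers treatment in general, and the surgical pathway (5.1, 5.2 and 6) supplies bloods on the day of surgery, the day after, and at 3 or 6 months, which do not depend on chemotherapy cycles.
- That a marker rising with progression would look flat. That requires an analysis restricted to women with the final sample, and section 5.5 sets no such rule. It is a risk left open by silence.

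It is also fair to say that the documents do not state that progressors stop early, nor the treatment setting, so no progression rate can be anchored in them. Finally, an extra blood would not answer the question alone: progression and regression are not defined, and 5.5 has no analysis of change.

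**Conclusion.** The gap is real but limited. As written, a woman whose chemotherapy ends before the last sampling cycle gives no end-of-treatment blood, and no section supplies a substitute. It is plausible, though not documented, that this happens more often with progression. The final change may then be observed mainly in completers. What is weakened is the chemotherapy part of one secondary outcome and the purpose stated in 5.1.

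The size is unknown. If stopping is rare and unrelated to progression (2% per cycle), 89% of women reach a post-cycle-6 blood and the harm is modest. If stopping is concentrated in progressors, as in the second illustration, their share falls from 25% to 9.5% and power from 0.49 to 0.19. The documents do not show which case applies. With at most 60 cancer patients, some of them archived samples, the chemotherapy group is likely to be small, so each lost progressor counts.

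**What to change.** First reconcile the cycle of the last blood between 5.1 and 6 (6th) and the 5.3 table (4th). Then, in 5.1, 5.3 and 6:

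- Keep the scheduled bloods. Add that, if chemotherapy ends before the last scheduled blood for any reason other than withdrawal of consent, that research blood is taken at the next routine visit.
- Record the number of cycles received, the date of each sample and the reason chemotherapy ended.

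In 5.5:

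- Keep the change from baseline to post-cycle 3 as the comparison at equal exposure.
- Report the change to the last available blood for all women who started chemotherapy and have a post-baseline sample. State that its timing differs by outcome, and give the number of women with no such sample.

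The cost is an amendment to the sampling text, the table and the analysis section, which can be made together with the cycle correction. The maximum number of draws does not rise, completers' samples do not change, treatment is unaffected, and routine visits fit the aim in section 7.4. The downside is that end-of-treatment samples will follow differing numbers of cycles; recording this makes it visible but does not remove it.

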#### 3. THEORITICAL FRAMEWORK

As the incidence of endometrial cancer continues to rise there is a health need for a better diagnostic and prognostic approach.

Studying the different biomarker levels in blood and cancer tissue will enable us to look for new targets that may be useful in the treatment and prognostication of this cancer.

Also, if the levels of these markers change significantly post-treatment, we can investigate if it will be possible to use these markers to assess response to treatment as follow-up for risk of recurrence forms an important part of the treatment protocol.

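### The chemotherapy visit table puts the last blood sample after cycle 4, whereas Sections 5.1 and 6 put it after cycle 6

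*Combined protocol and SAP*

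**What the plan says.** The chemotherapy blood schedule is stated in three places in the combined protocol and SAP.

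- **Section 5.1 (Study design):** a baseline sample at the consultation, then samples "after 3 rd and 6 th chemotherapy cycles to assess any changes in the markers that may correlate with progression or regression of disease".
- **Section 6 (Study setting):** a sample at the first consultation, then "after 3rd (with the blood test before the fourth cycle of chemotherapy) and 6th cycles of chemotherapy".
- **Section 5.3 (chemotherapy flow-chart table):** visit 2 is before chemotherapy starts, visit 3 is after the 3rd cycle and visit 4 is after the 4th cycle. The row "Taking blood sample" is marked at all three visits, and visit 4 is the last column.

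These samples serve the second secondary outcome in Section 4.3: "To determine if the markers could be used as tools to assess effects of treatment". Section 3 gives the motive more generally: further use of the markers is to be explored "if the levels of these markers change significantly post-treatment".

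**The concern.** The table and the two text sections cannot both be followed with the samples that each provides for. The table has no visit after cycle 6, and the text has no sample after cycle 4. Staff often work from a visit table, so the heading acts as an operational instruction.

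At stake is the later on-treatment measurement, which Section 5.1 wants in order to relate marker change to the course of the disease. A sample missed after cycle 6 cannot be drawn later. If some women were sampled by the table and others by the text, the last visit would combine two different amounts of treatment under one label.

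There is also a compliance point. Section 8.6 requires deviations to be documented and reported, and treats frequent recurrence as unacceptable. As the protocol stands, a last sample taken at either cycle departs from some part of it.

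**Working it through.** The plan gives no figure to reproduce. The check compares the three statements and then works out the difference in timing.

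**Side by side**

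| Sample | Section 5.1 | Section 6 | Table 5.3 |
|---|---|---|---|
| Baseline | At consultation | At initial consultation | Before chemotherapy starts |
| First on treatment | After cycle 3 | After cycle 3, drawn before cycle 4 | After cycle 3 |
| Last | After cycle 6 | After cycle 6 | After cycle 4 |

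The first two rows are compatible. Only the third conflicts, which is 1 of 3 sampling points.

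**Does the mention of a fourth cycle in Section 6 reconcile them?** No. It says when the post-cycle-3 sample is drawn, namely with the blood test that precedes cycle 4. That is visit 3 in the table, not visit 4.

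**Is it left over from an amendment?** The protocol history (Section 12) lists telephone consultation, the control population, additional tests, more controls and a longer study. None concerns chemotherapy sampling.

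**Size of the difference, from the documents alone**

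- Gap between the two on-treatment samples: 4 − 3 = 1 cycle by the table; 6 − 3 = 3 cycles by the text.
- Shift of the last sample: 6 − 4 = 2 cycles earlier.
- Treatment reflected in the last sample: 4/6 = 67% of the cycles that the text intends.

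**In calendar time (assumption).** The documents give no cycle length. With 21 to 28 days per cycle, the gap is 1 × 3 to 1 × 4 = 3 to 4 weeks by the table, against 3 × 3 to 3 × 4 = 9 to 12 weeks by the text.

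**Women affected (assumption).** The number having chemotherapy is not stated. Section 7.3 says "We will aim to recruit 30-60 patients with diagnosed endometrial cancer in the study", and that count includes archived cases. With an assumed chemotherapy share of 10% to 50%, the range is 0.10 × 30 = 3 to 0.50 × 60 = 30. Archived cases would not be sampled prospectively, so these counts are upper bounds. The range is too wide to carry weight.

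**The case against.** The strongest reply is that this is a clerical slip with little inferential consequence. Two full sentences agree on cycle 6, one of them tied to a stated purpose, and the table heading is the single outlier. The reference to the fourth cycle in Section 6 may even be how the wrong number entered the table. The study is exploratory and run at one centre, with the principal investigator responsible for its conduct, so sampling under two schedules is not especially likely. Section 5.5 specifies no paired or change-from-baseline analysis, and neither the sample size nor any named test depends on the chemotherapy samples. The secondary outcome is also served by the surgical cohort. Figure 2, the chemotherapy pathway, is not reproduced in the text available and might settle the matter.

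Most of this stands, and it limits the size of the problem. A slip is the likeliest explanation, there is no evidence that time points have been mixed, and the assumed patient numbers should not drive the severity. The remark in Section 3 about change after treatment is general, not specific to chemotherapy. None of it removes the conflict. A reader of the table alone would take the last sample at the wrong time under the text and would have no prompt to take another. That the analysis is loosely specified does not help, because a sample that was never drawn cannot be supplied by any later analysis.

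**Conclusion.** The concern holds: the current text is inconsistent about when the last chemotherapy blood sample is taken, and the table is probably the part in error. If the table is followed, the post-cycle-6 measurement is lost and the chemotherapy part of the treatment-effect secondary outcome is weakened. The surgical schedule in Sections 5.1, 5.2 and 6 is consistent.

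The finding itself rests on no assumption; only its expression in weeks and in numbers of women does. Two limits apply. Figure 2 could not be checked, so the absence of a governing statement is established only for the visible text. The documents also do not say how many cycles are planned, so it cannot be said that the post-cycle-6 sample marks the end of treatment, only that it is the later of the two candidates. This should be fixed because the possible loss is permanent and the correction is very small.

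**What to change.** 1. Change the visit 4 heading in the Section 5.3 table to the 6th cycle, in line with Sections 5.1 and 6. If the sponsor does intend cycle 4, amend those two sections instead.
2. Check that Figure 2 shows the same schedule.
3. Record the number of completed cycles with every chemotherapy sample and analyse by that number, not by the visit label. Any samples already taken after cycle 4 then remain usable and are not pooled with those taken after cycle 6.

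The first two steps resolve the inconsistency; the third protects data already collected. The cost is one heading, handled through the amendment route in Section 8.3, and one recorded field per sample. Compared with Sections 5.1 and 6, there are no extra visits, blood draws or patients.
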